**Table 10 Hepatotoxicity Management Guidelines**

Severity of LFT Elevation	Management Guideline

Grade 1 AST or ALT  <math>>ULN-3.0 \times ULN</math> if baseline was normal; <math>1.5-3.0 \times</math> baseline if baseline was abnormal or total bilirubin <math>>ULN-1.5 \times ULN</math> if baseline was normal; <math>>1.0-1.5 \times</math> baseline if baseline was abnormal
	
 
• Continue study drugs.
 
• Monitor LFTs until values resolve to baseline values.
 

Grade 2 AST or ALT  <math>>3.0-5.0 \times ULN</math> if baseline was normal; <math>>3.0-5.0 \times</math> baseline if baseline was abnormal or total bilirubin <math>>1.5-3.0 \times ULN</math> if baseline was normal; <math>>1.5-3.0 \times</math> baseline if baseline was abnormal
	
 
• Continue study drugs.
 
• The frequency of liver function test monitoring should be increased as clinically indicated if the investigator judges that the laboratory abnormalities are potentially related to study medication.
 


Grade 3 AST or ALT  <math>>5.0-20.0 \times ULN</math> if baseline was normal; <math>>5.0-20.0 \times</math> baseline if baseline was abnormal or total bilirubin <math>>3.0-10.0 \times ULN</math> if baseline was normal; <math>>3.0-10.0 \times</math> baseline if baseline was abnormal
	
 
• Interrupt ipatasertib until improvement of AST/ALT to Grade <math>\leq 2</math>. Treatment may be resumed at previous dose level.
 
• Continuation of rucaparib with elevation of AST/ALT up to Grade 3 is permitted provided bilirubin is <math>< ULN</math> and alkaline phosphatase is <math>< 3 \times ULN</math>. If levels do not decline within 2 weeks or they continue to rise, treatment interruption and improvement to Grade <math>\leq 2</math> will be required before rucaparib can be resumed with reduction by one dose level.
 
• Consider hepatology consult.
 
• Following treatment resumption, monitor serum transaminases and bilirubin at a minimum every 2 weeks for 3 months and monthly thereafter.
 
• If another Grade 3 event occurs, interrupt rucaparib and ipatasertib. On return of LFTs to Grade <math>\leq 2</math>, resume ipatasertib, reducing the dose by one level and rucaparib, reducing the dose by one level.
 
• Further Grade 3 occurrences must result in permanent discontinuation of rucaparib and ipatasertib.
 

Grade 4 AST or ALT <math>>20.0 \times ULN</math> if baseline was normal; <math>>20.0 \times</math> baseline if baseline was abnormal or total bilirubin <math>>10.0 \times ULN</math> if baseline was normal; <math>>10.0 \times</math> baseline if baseline was abnormal
	
 
• Permanently discontinue treatment with ipatasertib and rucaparib.
 

LFT=liver function test; QD=once daily; ULN=upper limit of normal.

If both study drugs are interrupted, step-wise reintroduction of one agent at a time (e.g., ipatasertib monotherapy for several days followed by reintroduction of rucaparib if liver enzymes remain Grade  $\leq 2$ ) may be pursued.

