#### 5.1.4.8 Hepatotoxicity

Liver enzyme elevations have been associated with both ipatasertib and rucaparib administration.

Permanently discontinue rucaparib and ipatasertib for any patients who develop a concurrent elevation of ALT and/or AST greater than 3× baseline and total bilirubin greater than 2× ULN and/or clinical jaundice in the absence of biliary obstruction or other

causes responsible for the concurrent elevation, including patients having abnormal liver function tests that meet Hy's law criteria (see Section 5.3.5.6).

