#### 5.3.5.6 Abnormal Liver Function Tests

The finding of an elevated ALT or AST ( $>3 \times \text{baseline value}$ ) in combination with either an elevated total bilirubin ( $>2 \times \text{ULN}$ ) or clinical jaundice in the absence of cholestasis or other causes of hyperbilirubinemia is considered to be an indicator of severe liver injury (as defined by Hy's Law). Therefore, investigators must report as an adverse event the occurrence of either of the following:

- *Treatment-emergent ALT or AST  $>3 \times \text{baseline value}$  in combination with total bilirubin  $>2 \times \text{ULN}$  (of which  $\geq 35\%$  is direct bilirubin)*
- Treatment-emergent ALT or AST  $>3 \times \text{baseline value}$  in combination with clinical jaundice

The most appropriate diagnosis or (if a diagnosis cannot be established) the abnormal laboratory values should be recorded on the Adverse Event eCRF (see Section 5.3.5.3) and reported to the Sponsor immediately (i.e., no more than 24 hours after learning of the event), either as a serious adverse event or an adverse event of special interest (see Section 5.4.2).

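### Table 10, Grade 3 row: a patient can enter on bilirubin alone, but the first-event ipatasertib hold names no bilirubin level for restart

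*Combined protocol and SAP*

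**What the plan says.** **Entry to the row.** Table 10 defines each grade by AST/ALT or bilirubin; the linking words are "baseline if baseline was abnormal or total bilirubin". In the Grade 3 row the bilirubin limb is above 3.0 and up to 10.0 times ULN for a normal baseline, or the same multiples of an abnormal baseline. Either limb is enough.

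**First event, ipatasertib.** The drug is held: "Interrupt ipatasertib until improvement of AST/ALT to Grade" ≤2. It may then restart at the same dose.

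**Repeat event.** Both drugs are held and restart one dose level lower: "On return of LFTs to Grade" ≤2. Appendix 1, footnote t, places total and direct bilirubin in the liver function panel.

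**After restart.** The row asks sites to track bilirubin: "Following treatment resumption, monitor serum transaminases and bilirubin at a minimum every 2 weeks for 3 months and monthly thereafter".

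**Step-wise note under the table.** If both drugs are stopped, the example restarts ipatasertib alone, "followed by reintroduction of rucaparib if liver enzymes remain Grade" ≤2.

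**Permanent stop.** Section 5.1.4.8 stops both drugs for a "concurrent elevation of ALT and/or AST greater than 3× baseline and total bilirubin greater than 2× ULN" and/or jaundice, when no other cause explains it. Section 5.3.5.6, which defines the Hy's law pattern for reporting, requires ALT or AST above 3 times baseline in both limbs, including the one "in combination with clinical jaundice".

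**The concern.** The variable that puts the patient in the row is not the variable that lets the patient out. After a first Grade 3 bilirubin event with low transaminases, a site looking for the level at which ipatasertib may restart will not find one. Sites may then act differently, at full dose, on a liver signal. Section 3.3.1 states that the two drugs have not been given together before, and Section 9.4 plans about 20 sites.

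Nearby guidelines do not have this mismatch. First-event holds for diarrhea (Table 5), fasting glucose (Table 6) and nausea or vomiting (Table 7) are released on the toxicity that triggered them. What is at stake is consistent patient safety management, not an estimate.

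**Working it through.** There is no plan figure to reproduce. The check applies the Table 10 cut-offs and then looks for another provision that supplies the missing level.

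**1. Which patients are affected.** Take AST/ALT at or below 3 times baseline.
- Normal baseline (≤1.0 × ULN): 3 × baseline ≤ 3.0 × ULN, within the row headed "Grade 1 AST or ALT".
- Abnormal baseline: grading is by multiple of baseline, and Grade 2 starts above 3.0, so again at most Grade 1.

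Upper limit of the affected AST/ALT range (3 × baseline):

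| Baseline (× ULN) | Upper limit (× ULN) |
|---|---|
| 0.5 | 1.5 |
| 0.8 | 2.4 |
| 1.0 | 3.0 |
| 1.5 (entry limit, Section 4.1.1) | 4.5 |
| 2.5 (entry limit, liver metastases) | 7.5 |

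**2. Grade 3 bilirubin, and where the amended hold would end.** Range is above 3 × to 10 × the reference; release is at ≤3 × the reference.

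| Baseline bilirubin (× ULN) | Grade 3 (× ULN) | Release with fix (× ULN) |
|---|---|---|
| Normal (reference 1.0) | >3.0 to 10.0 | ≤3.0 |
| 1.5 (entry limit) | >4.5 to 15 | ≤4.5 |
| 3.0 (Gilbert's limit) | >9 to 30 | ≤9 |

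**3. Grid check.** Eight AST/ALT baselines (0.3 to 2.5 × ULN) and six multiples of baseline (0.5 to 3.0) give 48 AST/ALT combinations. These were crossed with 41 Grade 3 bilirubin combinations (baseline 0.4 to 3.0 × ULN): 48 × 41 = 1,968. In all 1,968, AST/ALT is at most Grade 1 and the permanent-stop threshold is not reached. A further 1,968 combinations with AST/ALT above 3 times baseline (and below Grade 4) all meet the numeric part of the stop rule. So 3 times baseline is the right boundary. These are grid points, not patient frequencies.

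**4. Hypothetical example.** ALT baseline 0.8 × ULN, now 2.0 × ULN: 2.0 / 0.8 = 2.5 times baseline, Grade 1. Bilirubin 4 × ULN from a normal baseline: Grade 3. The stop rule is not met, and the table gives no bilirubin level for restart.

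**5. Does another provision supply it?**
- Section 5.1.4.1 holds until Grade ≤2, but for rucaparib only.
- Section 3.1.2 interrupts treatment for a dose-limiting toxicity in the Part 1 window, sets no recovery grade, and exempts asymptomatic Grade 3 laboratory findings judged not clinically significant.
- Sections 4.6.1, 5.1.4 and 5.1.4.10 rest on judgment and set no bilirubin level.
- Section 4.5.8 lists results to be reviewed on Day 1 of each cycle for dosing; AST and ALT are listed, bilirubin is not.

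None gives a bilirubin recovery criterion for ipatasertib.

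**The case against.** **The release test need not be read as already met.** A patient whose AST/ALT never rose above Grade 1 has not improved to Grade ≤2, and one whose bilirubin is still Grade 3 remains in a row that says to interrupt. This stands. A reader might infer that the table permits restart while bilirubin is still Grade 3; the text does not establish that, since it can equally be read as ordering a hold with no stated end. The missing criterion is common to both readings.

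**Jaundice might be a separate trigger in the permanent-stop rule.** If so, jaundiced patients with no other cause would leave the gap. The reference to a concurrent elevation, and Section 5.3.5.6, favour tying jaundice to AST/ALT above 3 times baseline, but the latter is a reporting definition. Even on the wider reading, patients without jaundice remain.

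**An AST/ALT test may be deliberate.** Section 5.1.3 names AST/ALT elevation as a potential ipatasertib risk, and hyperbilirubinemia is not among the risks in Section 5.1.1. But no reason is given for admitting bilirubin to the row and then leaving it out of the first-event release.

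**The repeat-event rule is not an exact model.** The liver panel in Appendix 1 also lists alkaline phosphatase and LDH. That is correct; the fix adds bilirubin only, which is the other variable Table 10 grades.

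**Practical safeguards exist.** The tables are guidelines, institutional practice is allowed, the row suggests a hepatology consult, and unacceptable toxicity requires stopping. This stands, and it keeps the severity low.

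**Conclusion.** The point holds as a low-severity defect in a stated rule: for a first Grade 3 event on bilirubin alone, with AST/ALT at or below 3 times baseline, Table 10 has no bilirubin recovery criterion for restarting ipatasertib. It rests on reading the two limbs of the row as alternatives, which is how the row is worded, and on the jaundice limb of the stop rule needing raised AST/ALT.

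Three further inferences are not supported:
- *That bilirubin goes unmonitored until after restart.* It is in the chemistry panel drawn at screening and scheduled treatment visits (Appendix 1). The gap is in the decision rule, not in data collection.
- *That rucaparib shares the gap.* Section 5.1.4.1 gives it a general Grade ≤2 release, and its Table 10 bullet carries its own bilirubin condition.
- *That results are affected.* No endpoint or estimate depends on this bullet, and the documents give no rate of isolated bilirubin events, so frequency cannot be stated.

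This is a cheap improvement.

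**What to change.** In the Grade 3 row of Table 10, reword the first-event bullet: *Interrupt ipatasertib until AST/ALT and total bilirubin are Grade ≤2.* Optionally, in the step-wise reintroduction note, replace the reference to liver enzymes with *AST/ALT and total bilirubin*.

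The edit is one bullet, and optionally one note, in the next amendment. No new test or visit is needed.

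The cost is some longer ipatasertib holds after isolated bilirubin events. Under Sections 5.1.4.9 and 5.1.4.10 a hold for toxicity of more than 28 days means discontinuing ipatasertib unless the Medical Monitor approves a restart, so a slowly clearing bilirubin could end treatment. Grading against an abnormal baseline limits this. It also limits the protection: at the 3 × ULN Gilbert's entry limit, restart would be allowed at up to 9 × ULN.

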#### **5.1.4.9 Dose Modifications**

##### **Rucaparib Dose Modifications**

Potential dose reduction steps for rucaparib based on different current doses of rucaparib are shown in [Table 11](#). In Part 1, during the DLT evaluation period (Cycle 1), dose reductions of rucaparib are not allowed for reasons other than a DLT or a decision by the Sponsor based on emerging safety data.

In Part 1, during the DLT evaluation period (Cycle 1), dose interruptions of rucaparib are not allowed for reasons other than toxicity. Patients are eligible for safety and DLT evaluation of the dose cohort if they receive at least 70% of the planned total dose of each study drug within Cycle 1 or they experience a DLT at any time during Cycle 1. During the remainder of the study, treatment with rucaparib may be interrupted for up to 28 days (1 cycle) for toxicity or reasons unrelated to toxicity. If rucaparib is withheld because of adverse events for >28 days, the patient will be discontinued from rucaparib. If, however, in the judgment of the investigator, the patient is likely to derive clinical benefit from rucaparib after a hold of >28 days, study drug may be restarted with the approval of the Medical Monitor.

Once a RP2D has been established at the end of Part 1, those patients in Part 1 who are treated at a dose below the RP2D and are tolerating study drugs may be escalated to the RP2D at the discretion of the investigator with approval from the Medical Monitor.

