### **3.1.2 Definition of Dose-Limiting Toxicity**

A DLT will be defined as any of the following adverse events related to study treatments occurring during the DLT reporting period, which corresponds to the first cycle of study treatment (i.e., from Cycle 1, Day –7 to Day 28; Cycle 1 has 35 days):

- Any death related to study treatment
- Grade 4 neutropenia lasting for  $\geq 7$  days
- Grade  $\geq 3$  neutropenia complicated by fever  $\geq 38^{\circ}\text{C}$  or infection
- Grade 4 thrombocytopenia lasting for  $\geq 7$  days
- Grade  $\geq 3$  thrombocytopenia complicated by hemorrhage or that requires transfusion
- Study treatment-related Grade  $\geq 3$  non-hematologic toxicity (graded according to the NCI CTCAE, v5.0) except for the following:
  - Grade 3 fatigue, asthenia, fever, anorexia, or constipation
  - Grade 3 nausea, vomiting, or diarrhea that responds to maximal supportive care within 72 hours
  - Grade 3 rash that resolves to Grade 1 within 7 days with maximal supportive care
  - Grade 3 hyperglycemia that is controlled with subcutaneous insulin
  - *Grade 3 ALT or AST elevation that is not accompanied by a concurrent increase in bilirubin (i.e., greater than the upper limit of normal [ULN])*
  - *Any other Grade 3 laboratory abnormality that is asymptomatic and is deemed not to be clinically significant by the investigator*

Patients who miss seven or more doses of either ipatasertib or rucaparib during the DLT-evaluation period for reasons other than a DLT will be replaced. In addition, patients who are discontinued from the study prior to completing the DLT-evaluation period for reasons other than a DLT (e.g., disease progression, consent withdrawn) will also be replaced. If a patient experiences a DLT, study treatment will be interrupted immediately for that individual and a safety assessment will be conducted.

The NCI CTCAE v5.0 will be used to characterize the toxicity profile of the study treatments for all patients.

An interim analysis for safety (including DLTs) will be performed by the Sponsor prior to the Dose-Expansion Phase (Part 2) to assess data from all patients in the Dose-Escalation Phase (Part 1). The interim analysis will be completed after the last evaluable patient in Part 1 has completed the first cycle of treatment. The combination dose levels demonstrating acceptable safety will be carried forward to the Dose-Expansion Phase (Part 2) of the study.

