**Table 5 Diarrhea Management Guidelines**

Severity of Diarrhea	Management Guideline
Grade 1	
Continue study drugs at the current dose level.
 
Manage with loperamide 4 mg initially, and then 2 mg every 4 hours or after every unformed stool until after 12-hour diarrhea-free interval.
 
Dietary modifications such as avoiding any lactose-containing foods.
 
Hydration with 8–10 glasses of clear liquid such as broth and low-calorie electrolyte-enhanced drinks per day.

Grade 2	
Manage with loperamide as early as possible 4 mg initially, and then 2 mg every 4 hours or after every unformed stool until after 12-hour diarrhea-free interval.
 
Dietary modifications such as avoiding any lactose-containing foods.
 
Hydration with 8–10 glasses of clear liquid, such as broth and low-calorie electrolyte-enhanced drinks, per day.
 
For non-infectious diarrhea lasting more than 48 hours despite optimal loperamide treatment, manage with second-line anti-diarrheal agents, including, but not limited to Lomotil®, codeine, or octreotide, or as per institutional guidelines.
 
Interrupt ipatasertib. Rucaparib may be continued at the investigator's discretion. If diarrhea persists for >3 days following interruption of ipatasertib, rucaparib should also be interrupted. Ipatasertib and rucaparib can be resumed at the same dose or one dose lower per investigator evaluation upon improvement to Grade 1 or better.
 
Reduce ipatasertib and rucaparib by one additional dose level (see Table 3) for recurrent Grade 2 diarrhea.

Grade 3	
Rule out infectious etiology.
 
Treatment per Grade 2 management guidelines and supportive care.
 
Interrupt ipatasertib and rucaparib until diarrhea improves to Grade 1 or better.
 
Ipatasertib and rucaparib should be reduced by one dose level (see Table 3 and Table 4 ) when treatment is restarted.
 
For recurrent Grade 3 diarrhea, reduce ipatasertib and rucaparib dose by one additional dose level (see Table 3), or permanently discontinue ipatasertib and rucaparib per investigator discretion.

Grade 4	
Management as per Grade 3 guidelines. Permanently discontinue ipatasertib and rucaparib.

If both study drugs are interrupted, step-wise reintroduction of one agent at a time (e.g., ipatasertib monotherapy for several days followed by reintroduction of rucaparib if diarrhea remains Grade ≤ 1) may be pursued.

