**Table 6 Fasting Hyperglycemia Management Guidelines**

Severity of Fasting Hyperglycemia	Management Guideline
Fasting glucose value >ULN to 160 mg/dL (8.9 mmol/L)	
 
• Monitor fasting glucose per protocol.
 
• Consider home glucose monitoring.
 

Fasting glucose value > 160 to 250 mg/dL (>8.9–13.9 mmol/L)	
 
• Interrupt ipatasertib until the fasting glucose value decreases to ≤160 mg/dL.
 
• Initiate home glucose monitoring.
 
• Start oral anti-diabetic medications (e.g., metformin).
 
• If the patient is already on an oral anti-diabetic medication, the dose of ipatasertib should be reduced by one dose level (refer to Table 3).
 
• If the patient previously has not been receiving any oral anti-diabetic medication, ipatasertib may be resumed at the previous dose level with initiation of oral anti-diabetic medication.
 

Fasting glucose value 250 to 500 mg/dL (>13.9–27.8 mmol/L)	
 
• Interrupt ipatasertib until fasting glucose value decreases to ≤160 mg/dL.
 
• Initiate home glucose monitoring.
 
• Treat hyperglycemia as per standard of care.
 
• Start (or increase dose of) oral anti-diabetic medications (e.g., metformin).
 
• If the patient is already on an oral anti-diabetic medication, ipatasertib should be reduced by one dose level when treatment is restarted.
 
• If previously the patient has not been receiving any oral anti-diabetic medication, ipatasertib may be resumed at the previous dose level with initiation of oral anti-diabetic medication.
 
• If fasting glucose value between 250 and 500 mg/dL recurs, the dose of ipatasertib should be reduced by one dose level when treatment is restarted.
 

Severity of Fasting Hyperglycemia	Management Guideline

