**Table 8 Rash Management Guidelines**

Severity of Rash	Management Guideline
Grade 1	
 
• Continue study drugs.
 
• Consider topical corticosteroids.
 

Grade 2	
 
• Interrupt ipatasertib and rucaparib treatment until resolution to Grade 1 or better or the toxicity is no longer clinically significant.
 
• Treat rash with topical corticosteroids.
 
• Consider treatment of rash with oral corticosteroids
 
• Follow above guidance and reduce ipatasertib by one dose level for recurrent Grade 2 rash.
 

Grade 3	
 
• Interrupt ipatasertib and rucaparib treatment until resolution to Grade 1 or better or the toxicity is no longer clinically significant.
 
• Treat rash with topical and systemic corticosteroids.
 
• Consider dermatological consultation.
 
• If the skin toxicity resolves to Grade 1 or better or is no longer clinically significant within 28 days, following completion of the steroid taper, ipatasertib and rucaparib may be resumed at one dose level below the previous dose (refer to Table 3).
 
• If recovery of the skin toxicity to Grade 1 or better does not occur or skin toxicity remains clinically significant continuously for 4 weeks, or Grade 3 rash recurs, permanently discontinue ipatasertib and rucaparib.
 

Grade 4	
 
• Administration of systemic steroids (oral or intravenous) is recommended. Consider dermatological consultation and skin biopsy. Ipatasertib and rucaparib should be permanently discontinued.
 

If both study drugs are interrupted, step-wise reintroduction of one agent at a time (e.g., ipatasertib monotherapy for several days followed by reintroduction of rucaparib if rash remains Grade  $\leq 1$ ) may be pursued.

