#### **Ipatasertib Dose Modifications**

The ipatasertib dose reduction instructions provided in [Table 12](#) are intended to serve as recommended guidelines to allow ongoing treatment for patients without signs or symptoms of disease progression while monitoring patient safety. Guidelines for implementing dosage modifications and treatment interruption or discontinuation for patients who experience specific adverse events are provided in [Section 5.1.1](#).

In Part 1, during the DLT evaluation period (Cycle 1), dose reductions of ipatasertib are not allowed for reasons other than a DLT or a decision by the Sponsor based on emerging safety data.

In Part 1, during the DLT evaluation period (Cycle 1), dose interruptions of ipatasertib are not allowed for reasons other than toxicity. Patients are eligible for safety and DLT evaluation of the dose cohort if they receive at least 70% of the planned total dose of each study drug within Cycle 1 or they experience a DLT at any time during Cycle 1.

During the remainder of the study, treatment with ipatasertib may be interrupted for up to 28 days (1 cycle) for toxicity or reasons unrelated to toxicity. If ipatasertib is withheld because of adverse events for >28 days, the patient will be discontinued from ipatasertib. If, in the judgment of the investigator, the patient is likely to derive clinical benefit from ipatasertib after a hold of >28 days, study drug may be restarted with the approval of the Medical Monitor.

Once a RP2D has been established at the end of Part 1, those patients in Part 1 who are treated at a dose below the RP2D and are tolerating study drugs may be escalated to the RP2D at the discretion of the investigator with approval from the Medical Monitor.

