**Table 13 Part 1 and Part 2 Dose Modification**

	Part 1, Cycle 1	Part 1, Cycle 2+ and Part 2
Dose reduction	Only for DLT or Sponsor decision	For toxicity (see Table 11 and Table 12 for dose reductions)
Dose hold	For toxicity; must receive >70% doses to be evaluable for DLT	For up to 28 days a for toxicity or reasons unrelated to toxicity

DLT=dose-limiting toxicity.

a If a longer hold is required for slowly resolving toxicity, Sponsor approval is required.

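### The Part 1 Cycle 1 limit on dose reductions is not reconciled with the toxicity tables, and the plan does not say how a patient reduced in Cycle 1 for a non-DLT toxicity enters the one-third rule

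*Combined protocol and SAP*

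**What the plan says.** **The Cycle 1 limit.** For the Part 1 DLT evaluation period, Section 5.1.4.9 states for rucaparib that "dose reductions of rucaparib are not allowed for reasons other than a DLT or a decision by the Sponsor", the latter resting on emerging safety data. For ipatasertib it states that "dose reductions of ipatasertib are not allowed for reasons other than a DLT", again with a Sponsor decision as the alternative. Table 13 gives Part 1 Cycle 1 its own column, with the entry "Only for DLT or Sponsor decision". Reduction for toxicity appears in the other column, for Part 1 from Cycle 2 onward and for Part 2. Holds for toxicity are allowed in Cycle 1.

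**The toxicity tables.** None of these names a Part or a Cycle.
- Table 5, Grade 3 diarrhea: "Ipatasertib and rucaparib should be reduced by one dose level" on restart. Recurrent Grade 2 diarrhea also leads to a reduction of both drugs.
- Table 6, fasting glucose above 160 and up to 250 mg/dL in a patient already on an oral anti-diabetic: "the dose of ipatasertib should be reduced by one dose level".
- Table 8: "reduce ipatasertib by one dose level for recurrent Grade 2 rash".
- Table 9 requires a lower ipatasertib dose after recurrent Grade 2 pneumonitis. Table 10 requires a lower rucaparib dose when Grade 3 ALT/AST has not declined within 2 weeks or keeps rising.

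**What counts as a DLT.** Section 3.1.2 sets the non-hematologic threshold at Grade 3 and exempts, among others, "diarrhea that responds to maximal supportive care within 72 hours", Grade 3 hyperglycemia controlled with subcutaneous insulin, and Grade 3 ALT/AST without a concurrent bilirubin rise.

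**How the count is used.** Section 3.1.1.1 declares as RP2D the highest dose level with an acceptable safety profile and at least 6 patients of whom fewer than one-third have a DLT. A patient without a DLT is evaluable with at least 70% of the planned total dose of each drug (Section 5.1.4.9), and is replaced after missing seven or more doses of either drug for non-DLT reasons (Section 3.1.2).

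**The concern.** For the same event in the same patient, one part of the protocol bars a reduction and another directs it. A site working from the toxicity tables is never sent to the limit. For dose levels, Tables 5, 6, 8 and 9 refer mainly to Table 3, which describes rucaparib tablets; the reduction steps are in Tables 11 and 12.

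Two things are at stake. Sites may handle the same event differently within a cohort of about 6. And a patient whose dose was lowered because of toxicity can be carried forward as one of the DLT-free patients supporting the assigned dose, which is then taken to about 30 patients in Part 2.

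**Working it through.** **Design figures.** Four dose levels (Table 1) × about 6 patients = 24, which matches the stated Part 1 size. The 7-day run-in plus 28 days = 35 days, which matches Section 3.1.2.

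**Instructions side by side, for restart within Part 1 Cycle 1**

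| Event | DLT under 3.1.2? | Toxicity table | 5.1.4.9 / Table 13 |
|---|---|---|---|
| Grade 3 diarrhea responding within 72 hours | No | Reduce both drugs (Table 5) | No reduction without a Sponsor decision |
| Recurrent Grade 2 diarrhea | No, below Grade 3 | Reduce both drugs (Table 5) | Same |
| Recurrent Grade 2 rash | No, below Grade 3 | Reduce ipatasertib (Table 8) | Same |
| Fasting glucose >160 to 250 mg/dL, already on oral therapy | No, if below Grade 3, or Grade 3 controlled with subcutaneous insulin | Reduce ipatasertib (Table 6) | Same |
| Recurrent Grade 2 pneumonitis | No, below Grade 3 | Reduce ipatasertib (Table 9) | Same |
| Grade 3 ALT/AST, no bilirubin rise, not declining in 2 weeks or still rising | No | Reduce rucaparib (Table 10) | Same |

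The glucose row is conditional because Section 5.1.4.4 says that Table 6 is not a grading scale.

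**Does a reduced patient stay evaluable?**

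Planned Cycle 1 doses:
- Ipatasertib once daily for 35 days: 35.
- Rucaparib twice daily for 28 days, starting on the evening of Day 1 (Section 4.3.2.2): 28 × 2 − 1 = 55.

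Fraction received = (doses at full level × full dose + doses at reduced level × reduced dose) / (planned doses × full dose). Reduction steps come from Tables 11 and 12. Assumptions: held doses count as missed, and both drugs are held together.

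Illustration: full dose to Day 10, hold on Days 11 to 13, reduced on Days 14 to 28.
- Rucaparib has 10 × 2 − 1 = 19 full, 6 missed and 30 reduced doses.
  - 600 to 500 mg: (19 × 600 + 30 × 500) / (55 × 600) = 26,400 / 33,000 = 80.0%.
  - 400 to 300 mg: (19 × 400 + 30 × 300) / (55 × 400) = 16,600 / 22,000 = 75.5%.
- Ipatasertib has 7 + 10 = 17 full, 3 missed and 15 reduced doses.
  - 400 to 300 mg: (17 × 400 + 15 × 300) / (35 × 400) = 11,300 / 14,000 = 80.7%.
  - 300 to 200 mg: (17 × 300 + 15 × 200) / (35 × 300) = 8,100 / 10,500 = 77.1%.

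All exceed 70%, and 6 and 3 missed doses are below seven. The patient is evaluable and DLT-free.

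**Range over timing**

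| Hold | Rucaparib 600→500 | Rucaparib 400→300 | Ipatasertib 400→300 | Ipatasertib 300→200 | Missed (rucaparib, ipatasertib) | Status |
|---|---|---|---|---|---|---|
| 3 days from Day 8 | 78.2% | 72.7% | 78.6% | 74.3% | 6, 3 | Evaluable |
| 3 days from Day 11 | 80.0% | 75.5% | 80.7% | 77.1% | 6, 3 | Evaluable |
| 3 days from Day 15 | 82.4% | 79.1% | 83.6% | 81.0% | 6, 3 | Evaluable |
| 7 days from Day 8 | 66.1% | 61.8% | 70.0% | 66.7% | 14, 7 | Replaced |

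A 3.5-day hold of rucaparib already gives seven missed doses, so when both drugs are held the evaluable case needs a hold of 3 days or less. Very early events can also fail the 70% rule: a 3-day hold from Day 2 leaves 67.3% for rucaparib 400 to 300 mg, from (1 × 400 + 48 × 300) / 22,000. Table 6 addresses ipatasertib only, so there up to 6 held days are possible. A 6-day hold from Day 11 leaves (17 × 400 + 12 × 300) / 14,000 = 74.3%, or (17 × 300 + 12 × 200) / 10,500 = 71.4%, still evaluable.

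**Effect on the one-third rule, cohort of 6.** 1/6 = 16.7% meets it; 2/6 = 33.3% is not below one-third and does not. Suppose one patient is reduced in Cycle 1 without a DLT. With no DLT among the other five, the result is 0/6 or, if that patient is counted as not tolerating the dose, 1/6; both meet the rule. With one DLT among the other five, it is 1/6 or 2/6, and the outcome changes.

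**The case against.** The case against is substantial, and most of it limits the point without removing it.

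- **Specific over general.** The Cycle 1 wording is scoped to its period, and Table 13 places reduction for toxicity outside Part 1 Cycle 1. Section 5.1.4 presents the tables as guidelines and allows institutional practice. This makes precedence of the Cycle 1 limit the natural reading. But it is an inference: no precedence is stated, and the tables use directive wording.
- **A reader might infer that sites cannot comply with both instructions.** The documents do not go that far. A Sponsor decision is a permitted route and holds for toxicity are allowed, so a site need not choose between restarting at full dose and breaching the protocol. Still, the Sponsor route rests on emerging safety data, with no per-patient request process described, and a long hold leads to replacement.
- **A reader might infer that the DLT count is ambiguous.** It is not. Section 3.1.2 defines a DLT by event, grade, relatedness and window, so responsive Grade 3 diarrhea is not one whether or not the dose is later lowered. By the plan's own rule the result stays 1/6.
- **Other safeguards.** A reduction against Section 5.1.4.9 would be a protocol deviation, reviewed under Section 9.2. Section 6.2 evaluates major deviations and Section 6.5 flags dose modifications. RP2D selection also needs an acceptable safety profile, and safety and PK are reviewed before Part 2. So the patient would probably be seen; none of these sections says how the patient enters the one-third rule.
- **Chosen example.** With both drugs held, the illustration lies one rucaparib dose below the replacement limit. That is correct, and is why a range is shown.

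**Conclusion.** The point holds as an unreconciled instruction plus an unstated analysis rule. It is worth correcting, but it is not a flaw in the DLT definition or in the RP2D threshold.

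Its size is at most one patient's classification per affected patient. In a cohort of 6 this matters only when exactly one other patient has a DLT. In the evaluable scenarios with both drugs held for 3 days, from Day 8, 11 or 15, the reduced patient has received roughly 73% to 84% of the planned dose while standing as DLT-free at the assigned level. These figures rest on assumed onset, hold length and the counting of held doses as missed. Longer holds, and some very early events, remove the patient from the evaluable set. The documents give no frequency for such events, so no probability of a changed RP2D is claimed.

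**What to change.** 1. Reconcile Section 5.1.4.9 and Table 13 with Tables 5, 6, 8, 9 and 10. State in each table which instruction applies in Part 1 Cycle 1, and refer to the limit there. Which instruction applies is for the sponsor to decide.
2. State how a patient reduced in Cycle 1 for a non-DLT toxicity is handled in the DLT-evaluable set and in the one-third rule.
3. In the RP2D summary, flag every patient reduced in Cycle 1 for treatment-related toxicity. As a sensitivity line only, show the cohort result with and without counting that patient as tolerating the assigned dose. The primary count under Section 3.1.2 is unchanged.

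The cost is wording in one section, Table 13 and five table footnotes, plus one line in the RP2D summary. No extra patients or visits are needed. The downside is that the RP2D summary may look slightly less favourable.
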